Despite the high success rate of anti-reflux surgery, reoperation does occur. The indication for reoperation is most often recurrence of reflux symptoms or dysphagia, and reoperation should be preceded by thorough investigation and possible endoscopic balloon-dilation (15). Laparoscopic reoperation is both feasible and safe, but has been linked to higher morbidity, higher risk of conversion to open surgery and longer length of stay. The final result seem to result in less patient satisfaction than primary surgery, but the available evidence is limited by a high risk of bias due to small sample size and a possible underreporting of complications (16, 17).

An American study reported a cumulative five- and ten year incidence of reoperation of 5.2% and 6.9% respectively. The rate of reoperation was highest in the first year after primary anti-reflux surgery. 30% of reoperations were performed in a different center than the primary procedure. In a Danish study, Funch-Jensen et al (18), investigated rate of reoperation in Denmark 1997-2005 and calculated a rate of 5% without significant differences in length of stay, rate of complications or mortality compared to primary

surgery. Reoperation was however associated with a higher rate of conversion to open surgery with a tendency towards higher rates of conversion in low-volume centers. As in the American study, reoperation was often performed at different centers than the primary procedure. Whether this was the result of centralization or patient's wishes is unknown.

It is our hypothesis, that from 2000-2017, reoperative anti-reflux surgery was performed primarily with a laparoscopic approach without increased length of stay or rate of complications compared to primary surgery. Due to increased surgical experience the rate of complications is decreasing despite increased comorbidity. Endoscopic balloon-dilatation delays reoperation but does not prevent it.

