## Statistical analysis

### 1) Course of illness leading to reoperative anti-reflux surgery

Data will be analyzed using STATA15. Descriptive analysis of age, sex, comorbidity (Charlson Comorbidity Index, ASA-score, BMI, alcohol/tobacco use), complications to surgery, rate of endoscopic dilation and mortality comparing patients with only primary anti-reflux surgery and patients with reoperation during the study period, will be performed using Student's t-test, Chi2-test and Mann-Whitney-U test.

Logistic regression will be performed with reoperation (laparoscopic, open or other) as primary outcome and age, sex, comorbidity (Charlson Comorbidity Index, ASA-score, BMI, alcohol/tobacco use), complications to surgery and endoscopic or surgical procedure during study period as independent variables. If the number of patients is sufficient, subanalysis will be performed with emergency reoperation as dependent variable/outcome.

Secondary analysis will be performed using Cox-regression investigating time to reoperation with age, sex, comorbidity (Charlson Comorbidity Index, ASA-score, BMI, alcohol/tobacco use), complications to surgery and endoscopic or surgical procedure during study period as independent variables.

*2) Utilization of treatment of gastroesophageal reflux disease.*

The rate of anti-reflux surgery per 100.000 inhabitants for each year during the study period will be calculated using census data from Statistics Denmark. From MEDSAT the rate of use of pharmacological anti-reflux treatment per 100.000 inhabitants will be calculated using abovementioned census-data. Trends in the utilization of surgery are investigated with trend-analysis in the form of Poisson-regression alternatively negative binominal regression.

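### Student's pooled-variance t-test is named for a descriptive comparison of very unequal groups (about 13.5:1 to 19:1 on the cited rates); Welch's t-test would be safer at almost no cost

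*Combined protocol and SAP*

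**What the plan says.** Under Statistical analysis, part 1 (Course of illness leading to reoperative anti-reflux surgery), the plan describes a two-group table, "comparing patients with only primary anti-reflux surgery and patients with reoperation during the study period". The variables begin with "Descriptive analysis of age, sex, comorbidity (Charlson Comorbidity Index, ASA-score, BMI, alcohol/tobacco use" and continue with surgical complications, endoscopic dilation and mortality. The tests for this table are "Student's t-test, Chi2-test and Mann-Whitney-U test".

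The section does not say which variable gets which test. It does not mention equal or unequal variances, and it plans no confidence intervals for this comparison. On software it says "Data will be analyzed using STATA15", with no option for the t-test.

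The main inference lies elsewhere: "Logistic regression will be performed with reoperation (laparoscopic, open or other) as primary outcome", followed by a secondary Cox regression for time to reoperation.

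The documents give no expected group sizes. The only guide is the Background, where an American study is cited for a "cumulative five- and ten year incidence of reoperation of 5.2% and 6.9% respectively" and an earlier Danish study "calculated a rate of 5% without significant differences in length of stay".

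**The concern.** The sizes of the two groups are set by how often reoperation happens, and on the cited figures it is uncommon. In a pooled-variance test with one large and one small group, the variance estimate comes almost wholly from the large group, while the sampling error of the difference in means comes almost wholly from the small one. If the two groups have different spreads, the standard error is therefore wrong. It is too large when the small group is less variable, so real differences are missed. It is too small when the small group is more variable, so chance differences are declared significant.

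The distortion depends on the ratio of the group sizes and not on their total, so nationwide coverage does not remove it. What is at stake is the reading of the descriptive table: which baseline means appear to differ between reoperated and other patients.

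**Working it through.** The plan states no sample size, power, significance level or SD, so there is no design figure to reproduce.

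**Inputs**
- Reoperated share *p*: 5% (earlier Danish study), 5.2% and 6.9% (American study at five and ten years), all from the Background.
- SD ratio *r* = SD(reoperated) / SD(primary only): assumed.
- Two-sided 5% level: assumed.

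**Step 1: group ratio**, (1 − p)/p.
- 0.95/0.05 = 19.0
- 0.948/0.052 = 18.2
- 0.931/0.069 = 13.5

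**Step 2: true and estimated variance.** Write q = 1 − p and set the primary-only SD to 1. Apart from a common factor 1/N, the large-sample variances of the difference in means are:
- true: 1/q + r²/p
- as estimated by pooling: (q + p·r²)(1/q + 1/p)

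With k² = true/estimated, the actual level is 2[1 − Φ(1.96/k)].

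At p = 0.05 and r = 1, the reoperated group supplies 20 of the 21.05 units of true variance (95%) but has only 5% of the weight in the pooled estimate.

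**Step 3: two cases in full, p = 0.05.**
- r = 1.2: true = 1.053 + 28.8 = 29.85; estimated = 1.022 × 21.05 = 21.52; k² = 1.387, k = 1.178; 1.96/1.178 = 1.664; level 9.6%.
- r = 0.8: true = 1.053 + 12.8 = 13.85; estimated = 0.982 × 21.05 = 20.67; k² = 0.670, k = 0.819; 1.96/0.819 = 2.39; level 1.7%.

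**Step 4: actual level of a nominal 5% Student's test.**

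| SD ratio | 19:1 | 13.5:1 | 1:1 |
|---|---|---|---|
| 0.80 | 1.7% | 1.8% | 5.0% |
| 0.90 | 3.1% | 3.2% | 5.0% |
| 0.95 | 4.0% | 4.1% | 5.0% |
| 1.00 | 5.0% | 5.0% | 5.0% |
| 1.05 | 6.1% | 6.0% | 5.0% |
| 1.10 | 7.2% | 7.1% | 5.0% |
| 1.20 | 9.6% | 9.4% | 5.0% |

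The 1:1 column shows that the imbalance is what exposes the test to unequal spread. Between 13.5:1 and 19:1 the exact ratio hardly matters.

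**Step 5: simulation.** Normal data, assumed sizes 1,900 and 100, 20,000 runs per setting.

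| SD ratio | Student | Welch |
|---|---|---|
| 0.8 | 1.8% | 5.2% |
| 0.9 | 3.2% | 5.3% |
| 1.0 | 5.1% | 5.1% |
| 1.1 | 7.1% | 4.7% |
| 1.2 | 9.8% | 5.0% |

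Student's test follows the formula. Welch's test stays close to 5% throughout, and at equal SDs the two tests have the same level.

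**The case against.** Several objections are fair and limit the point.

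- **The text does not say equal variance.** Student's t-test may be used loosely for any two-sample t-test. That is possible, but the pooled test is the standard meaning and also Stata's default, so the plan read literally leads there.
- **No variable is assigned to the t-test.** Age and BMI are the natural candidates. The other variables are mostly categorical, ordinal or skewed, and Mann-Whitney is also available. So few comparisons are affected, and which ones is an inference.
- **Nothing shows that the spreads differ.** The documents contain no SDs. That reoperated patients are a selected subgroup makes unequal spread plausible but does not establish it. The levels above show sensitivity, not a demonstrated error.
- **Mann-Whitney is also affected.** At 1,900 versus 100, in 2,000 simulated runs, its rejection rate was 2.6% at an SD ratio of 0.8 and 6.6% at 1.2. This is a smaller departure, and replacing the t-test does not address it.

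A reader might also infer more than the documents support:

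- **That any difference in spread invalidates the test.** A 5% difference in SD moves the level only to 4.0% or 6.1%.
- **That 19:1 is this study's ratio.** It comes from the earlier Danish study's 5%. The cited rates span 13.5:1 to 19:1, and this cohort's split is unknown.
- **That planned confidence intervals would be wrong.** None is planned for this comparison.
- **That the study's main conclusions are at risk.** The logistic and Cox models do not use the t-test, and their covariates are listed in advance and not chosen from the descriptive p-values.

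**Conclusion.** The point holds as a minor, nearly free improvement. At the imbalance suggested by the cited reoperation rates, a 20% larger SD among reoperated patients would roughly double the false-positive rate of Student's test (9.6% at 19:1), and a 20% smaller SD would cut it to about a third of nominal (1.7%). Differences of 10% give 7.2% and 3.1%.

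These figures assume a two-sided 5% level, SD ratios that the documents neither give nor exclude, and a split in this cohort close to that of the earlier studies. The consequence is confined to descriptive comparisons of means. The primary and secondary regression analyses are unaffected.

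**What to change.** In Statistical analysis, part 1, replace Student's t-test with Welch's unequal-variance t-test for comparisons of means such as age and BMI. In the same sentence, state which variables are compared by Welch's test, which by Mann-Whitney and which by chi-square, so that it is clear where the change applies. If confidence intervals for differences in means are reported later, use the Welch form for those too.

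The cost is one word in the plan and the unequal-variance option of the t-test command in Stata. No further data are needed. In the simulation at equal SDs both tests held the same level (5.1%); power was not compared.

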## Methods

The study is a two-part register-based cohort study based on data from The National Patient Registry, The Civic Registry and Danish Anaesthesia Database in the period 1996-2017. The two individual parts of the study concerns the same population.

The population is defined as all adult Danish patients undergoing anti-reflux surgery (Nomesco: KJBC00, KJBC01, KJBC02, KJBW96, KJBW97) from 2000-2017 identified from The National Patient Register.

Age, sex, Charlson Comorbidity Index at date of surgery and length of stay in relation to any surgery and any surgical or endoscopic procedure performed after anti-reflux surgery (including diagnosis 30 days postoperatively to establish possible morbidity) are derived from the National Patient Registry.

ASA-score, weight, height, use of alcohol or tobacco and priority of any surgery (emergency or planned) during the study period are retrieved from The Danish Anaesthesia Database. From the Civic Register, data on mortality in the study period are retrieved.

Information on the use of pharmacological treatment for gastroesophageal reflux disease on population level is retrieved from MEDSTAT and data on population size on population level are retrieved from Statistics Denmark.

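### Both reoperation models use procedures done after the index operation without fixing when they count; the lead logistic model cannot time them and has no horizon

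*Combined protocol and SAP*

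**What the plan says.** In the Statistical analysis section, part 1, the lead model is given as: "Logistic regression will be performed with reoperation (laparoscopic, open or other) as primary outcome". No time window, minimum follow-up, offset for follow-up or year of index operation is mentioned. The covariate list ends with "complications to surgery and endoscopic or surgical procedure during study period as independent variables".

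The time-to-event model comes second: "Secondary analysis will be performed using Cox-regression investigating time to reoperation". It carries the same covariate list. Time-dependent coding, a landmark, a restriction to procedures before reoperation, and the exclusion of the reoperation from the procedures are not mentioned for either model.

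The Methods section shows where the procedure variable comes from: the extract covers "any surgical or endoscopic procedure performed after anti-reflux surgery". The cohort is adults "undergoing anti-reflux surgery (Nomesco: KJBC00, KJBC01, KJBC02, KJBW96, KJBW97) from 2000-2017", and the registers are used for 1996-2017. Deaths are collected ("From the Civic Register, data on mortality in the study period are retrieved") but have no stated role in either regression.

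The Background cites the only reoperation rates in the document ("An American study reported a cumulative five- and ten year incidence of reoperation of 5.2% and 6.9% respectively") and says that "reoperation should be preceded by thorough investigation and possible endoscopic balloon-dilation". It also hypothesises that balloon dilatation postpones reoperation without averting it.

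**The concern.** A procedure done after the index operation is not known at time zero. Whether a patient has one depends on how long that patient is observed, and reoperation may end the period in which procedures are counted.

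- **Counted only before reoperation:** patients who are never reoperated have more time to acquire a procedure. The procedure then looks protective even if it does nothing (immortal-time bias).
- **Counted at any time:** procedures after reoperation are credited to the period before it. The estimate then reflects how often patients are treated after the outcome.

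At stake is the reading of the dilatation and procedure estimates, which bear directly on the stated dilatation hypothesis. An analyst who follows the text could report an association on either side of 1 for a procedure with no effect.

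The missing horizon is a separate and smaller matter. Patients operated on in 2000 can be observed for about 18 years and those operated on late in 2017 for almost none. A covariate that becomes more or less common over the entry years is therefore partly a marker of follow-up time.

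**Working it through.** The plan gives no sample size, event count or power, so there is no figure of its own to reproduce. The check asks what each counting rule returns when the true effect is known.

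**Inputs from the document.** Entry 2000-2017; end of data taken as the end of 2017 (inferred from the register period); reoperation 5.2% at 5 years and 6.9% at 10 years; rate highest in the first year.

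**Assumptions.** Even accrual over 18 years, no deaths, procedure rates constant at 0.5, 2 or 5% per year, and a Weibull curve through the two cited points.

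**Step 1, the curve.** F(t) = 1 - exp(-λt^k).
- k = ln[ln(1/0.931) / ln(1/0.948)] / ln 2 = ln(0.0715/0.0534) / 0.693 = 0.42
- λ = 0.0534 / 5^0.42 = 0.027
- F(1) = 2.7% and F(18) = 8.8%. The hazard falls with time, as the Background describes.

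**Step 2, a procedure with no effect, counted only before reoperation.** The chance of a procedure by time t is 1 - exp(-rt), with t ending at reoperation or at the end of follow-up. At r = 2% per year, averaging over simulated patients gives 5.5% exposed among the reoperated and 15.9% among the others. The odds ratio is (0.055/0.945) / (0.159/0.841) = 0.31. Across the three rates:

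| Analysis, true HR 1 | Estimate |
|---|---|
| Logistic OR | 0.29-0.34 |
| Cox HR, fixed ever/never covariate | 0.23-0.29 |

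With the covariate switched on at the procedure date, Cox gives 0.94-1.04 across all curves and procedure patterns tried.

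**Step 3, the same procedure, counted at any time.** The result now depends on the procedure rate after reoperation. If that rate is unchanged, OR is about 1.2-1.3 and fixed Cox HR about 1.0. If it ranges from half to double, OR runs 0.73-2.44 and fixed Cox HR 0.61-1.91.

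**Step 4, the missing horizon.** With mid-year entry and no true change over time, the observable risk is 8.7% for index year 2000, 5.4% for 2012, 3.9% for 2015 and 2.0% for 2017. The average over uniform entry is 6.2%. Take a covariate with no effect whose prevalence rises linearly from 10% to 20% over the entry years. Its prevalence is 14.15% among the reoperated and 15.06% among the others, so OR = (0.1415/0.8585) / (0.1506/0.8494) = 0.93. The other cases follow in the same way:

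| Prevalence over entry years | OR, true value 1 |
|---|---|
| 20% to 40% | 0.92 |
| 10% to 20% | 0.93 |
| 10% to 12.5% | 0.98 |
| no drift | 1.00 |

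Falling prevalence biases the odds ratio upward instead.

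**Step 5, what a 5-year horizon costs.** Index years 2013-2017 drop out: 5/18 = 28% of patients. The rest contribute 13/18 × 5.2% = 3.8% of the cohort as events, against 6.2% without a horizon, so about 60% of observed reoperations are kept.

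**The case against.** The strongest reply is that this is brevity and not error. The Cox paragraph does not say that procedures will be fixed covariates, and a careful analyst could code them by date without departing from the text. For the Cox model that stands: the fault is an open specification. It does not rescue the logistic model, which has no time axis and is the lead analysis.

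Four stronger readings are tempting and should not be drawn.

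- **That the plan would turn a harmful procedure into a protective one.** A fixed Cox HR below 1 despite a true threefold hazard arises only if procedures are counted before reoperation. The plan's wording spans the whole study period. If procedures count at any time and the rate is unchanged after reoperation, the same scenario gives 1.54-2.01, which is attenuated and not reversed.
- **That the reoperation counts as its own predictor and makes the odds ratio infinite.** The wording does not exclude it, but reoperation is named separately as the outcome, and any analyst would notice perfect prediction. This is a gap in wording.
- **That the missing horizon seriously distorts the baseline odds ratios.** The document gives no Danish drift figures and says it is unknown whether Denmark follows the American trends. The remark on increased comorbidity is not clearly about index patients. The planned Cox model already handles unequal follow-up.
- **That the fix would test the dilatation hypothesis.** The plan assigns that hypothesis to neither model. Dilatation also marks symptomatic patients, so even a correctly timed estimate remains an association.

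**Conclusion.** The concern holds and should be fixed before analysis. The main fault is the post-index procedure covariate: the lead model cannot time it, and the Cox text does not say how it is timed. With no true effect, the estimate can fall to about 0.3 (OR) or 0.23-0.29 (HR), or lie anywhere in about 0.7-2.4 (OR) or 0.6-1.9 (HR), depending on a choice that the plan does not make.

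These sizes rest on the Weibull curve through two American figures, even accrual, constant assumed procedure rates and no deaths. The structural fault does not depend on them. The net direction in the real data cannot be predicted, because confounding by indication works against immortal-time bias.

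The missing horizon is secondary: null odds ratios of about 0.92-0.98 for the assumed rises in prevalence, and 1.00 without drift.

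**What to change.** Make the planned Cox model the lead analysis of reoperation. Measure time from the index operation, censor at death and at end of data, and add year of index operation. Enter dilatation and other post-index procedures, excluding the reoperation itself, as separate time-dependent covariates switched on at the procedure date. State that they are associations subject to confounding by indication. Promoting Cox without the dated covariates would not cure the main fault.

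If a logistic model is kept, give it a fixed horizon (for example 5 years, index operations to the end of 2012) and leave post-index procedures out.

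The cost is low. Both models are already planned, and Cox already needs reoperation dates. The additions are procedure dates in the extract and time-dependent coding. A 5-year logistic model gives up about 28% of patients under even accrual. Starting the clock at day 30, censoring at emigration and reporting Aalen-Johansen cumulative incidence are optional refinements and not part of the error.

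### Neither reoperation model includes calendar year of the index operation, although the plan expects comorbidity and complications to change over 2000-2017 and, in the logistic model, year sets time at risk

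*Combined protocol and SAP*

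**What the plan says.** **Models.** Under Statistical analysis, part 1, the primary analysis reads "Logistic regression will be performed with reoperation (laparoscopic, open or other) as primary outcome and age, sex, comorbidity". Comorbidity is spelled out as Charlson index, ASA score, BMI and alcohol or tobacco use, and the list closes with "complications to surgery and endoscopic or surgical procedure during study period as independent variables". The second model reads "Secondary analysis will be performed using Cox-regression investigating time to reoperation with age, sex, comorbidity" and continues with the same variables. Neither list contains year, approach or priority of the index operation. The words laparoscopic, open or other describe the reoperation, which is the outcome.

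**Data.** Methods defines the cohort as adults "undergoing anti-reflux surgery (Nomesco: KJBC00, KJBC01, KJBC02, KJBW96, KJBW97) from 2000-2017". It scores the Charlson index at the date of surgery, so that date is held. It also states that "priority of any surgery (emergency or planned) during the study period are retrieved from The Danish Anaesthesia Database". Index approach is not listed as a variable; at most it can be inferred from the procedure codes.

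**Use elsewhere.** Year is used only in part 2, for annual rates and the trend regression. Priority enters the analysis only through a conditional "subanalysis will be performed with emergency reoperation as dependent variable/outcome".

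**Expected trends.** The hypothesis at the end of Background is that, with growing surgical experience, complications fall over the period even though comorbidity rises.

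**The concern.** The plan expects two of its own covariates, comorbidity and complications, to drift with calendar time, and then models reoperation without calendar time. Two mechanisms follow.

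- **Time at risk (logistic model).** No fixed window is stated for the outcome. If follow-up ends with the data in 2017, a patient first operated on in 2000 can be observed for more than 17 years and one operated on in 2017 for less than one. A characteristic that is more common in later years will look protective because those patients had less time to be reoperated. One that is more common in earlier years, as complications are expected to be, will look harmful for the same reason.
- **Era (both models).** If the underlying rate of reoperation changed over 18 years, covariates that track the calendar pick up part of that change. Cox regression deals with unequal follow-up by censoring, but not with era.

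The affected results are the odds and hazard ratios that part 1 exists to produce.

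**Working it through.** The documents give no sample size, event count, power or effect size, so there is no stated figure to reproduce. The check compares the covariate lists with the retrieved variables (above) and then illustrates the possible size.

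**A. Omitting year from the logistic model**

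Inputs from Background: cumulative reoperation of 5.2% at 5 years and 6.9% at 10 years in the cited American study.

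Assumptions:
- equal numbers of index operations each year, at mid-year, with follow-up to the end of 2017;
- first-year incidence *c* of 1.04% (a constant rate to year 5), 2% or 3%, with straight lines between points;
- beyond 10 years, the 5-to-10-year slope continues: (6.9 − 5.2)/5 = 0.34 percentage points per year;
- a comorbidity indicator with no true effect, whose prevalence changes linearly from 2000 to 2017.

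Risk observed by the end of 2017:
- Index 2000 (17.5 years): 6.9 + 7.5 × 0.34 = 9.45%.
- Index 2014 (3.5 years): *c* + (2.5/4)(5.2 − *c*) = 3.64%, 4.00% and 4.37% for the three values of *c*.
- Index 2017 (0.5 years): 0.5 × *c* = 0.52%, 1.0% and 1.5%.

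With prevalence p_y and risk r_y in year y, the pooled risks are R1 = Σp_y r_y / Σp_y with the factor and R0 = Σ(1−p_y) r_y / Σ(1−p_y) without it. The odds ratio is [R1/(1−R1)] / [R0/(1−R0)].

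| Prevalence 2000 → 2017 | Odds ratio, *c* = 1.04% | *c* = 2% | *c* = 3% |
|---|---|---|---|
| 20% → 20% | 1.00 | 1.00 | 1.00 |
| 20% → 30% | 0.93 | 0.94 | 0.94 |
| 20% → 40% | 0.88 | 0.89 | 0.90 |
| 10% → 40% | 0.80 | 0.82 | 0.84 |

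For example, 20% → 40% with *c* = 1.04% gives R1 = 5.58% and R0 = 6.29%, so (0.0558/0.9442)/(0.0629/0.9371) = 0.88. Within any single year the odds ratio is 1.00 by construction, so adjusting for year removes the distortion.

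**B. Omitting index approach or priority**

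Every input here is assumed: 5% baseline risk (in line with the cited Danish rate), a patient factor with no direct effect, and an odds ratio for approach or priority of 1.5 to 3. With odds ratio 2 and shares of 40% and 20% in patients with and without the factor, the higher risk is 0.1053/1.1053 = 9.52%. Then R1 = 0.4 × 9.52 + 0.6 × 5 = 6.81%, R0 = 0.2 × 9.52 + 0.8 × 5 = 5.90%, and the odds ratio is 1.16.

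| Share with / without the factor | Odds ratio of patient factor (approach or priority OR 1.5 to 3) |
|---|---|
| 30% / 20% | 1.05 to 1.14 |
| 40% / 20% | 1.09 to 1.28 |
| 10% / 5% | 1.02 to 1.08 |

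Both tables are two-variable calculations. The planned models also adjust for age, sex and the other covariates, which could absorb some of the distortion. A and B also point in opposite directions, so a net direction cannot be claimed.

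**The case against.** **The covariate list may already cover the index operation.** Surgical procedure during the study period could be read that way. Methods, however, describes the retrieved procedures as those done after anti-reflux surgery, and the wording would not cover year on either reading.

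**A reader might infer that the patient-factor effects are confounded by the operation received, and that approach and priority belong in the main model.** The documents do not support this.
- Age, sex, comorbidity and BMI precede the choice of operation. Approach is therefore partly on the path from these factors to reoperation, and adjusting for it changes the quantity estimated from a total effect towards a direct one.
- The spread of laparoscopy described in Background is American, dates from 1990-2000, and concerns perioperative outcomes. Background adds that the laparoscopic share has since been stable at 80% and that Danish trends are unknown. Nothing there links index approach to later reoperation.
- Of the three variables, only priority is explicitly retrieved as such. Year follows from the surgery date. Whether approach and conversions can be read from the codes, and how complete they are, is not stated.

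This objection stands for age, sex, comorbidity and BMI. It is weaker for complications: approach and priority precede the complication and may plausibly affect both it and reoperation, which is ordinary confounding. The models also already condition on complications, a post-operative variable, so they do not give clean total effects of comorbidity as written.

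**Extra terms are not free when events are few.** This is fair, and it governs how year should be entered.

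**Conclusion.** The point holds for calendar year. Both models omit it, the plan itself expects comorbidity and complications to move with it, and in the logistic model it also fixes time at risk. Under the stated assumptions a null comorbidity odds ratio moves to about 0.80-0.94. With no prevalence trend the follow-up mechanism has no effect. The Danish incidence curve, the yearly numbers of operations and the prevalence trends are not in the documents, so the true size cannot be determined.

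For index approach and priority the conclusion is narrower. They are plausible confounders of the complications term, and their role should be stated. The documents do not establish that leaving them out biases the patient-factor coefficients, and the 1.02-1.28 range rests wholly on assumed inputs. Nor do the aim or hypotheses ask how index approach relates to reoperation.

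**What to change.** 1. Add year of index surgery to both the logistic and the Cox model, as a spline or as categories, and fix the form in advance. Single-year indicators would take 18 − 1 = 17 terms, and the last years will hold few events, so a spline or grouped periods is more economical.
2. As a further model, reported beside the first, add index priority (already retrieved) and index approach where the procedure codes allow it. State that the main purpose is to adjust the complications term, and that the coefficients for age, sex, comorbidity and BMI then exclude any effect acting through approach or priority.
3. State how missing priority is handled, and report the number of patients in each model.

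The cost is wording and a few model terms, with no new data source. The downsides are lower precision, given an expected reoperation incidence of about 5-7%, and possible loss of patients from the further model where priority is missing. The model with year does not depend on priority.
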